12.2. Pivotal Phase

12.2.1. Planned Analyses

The paroxysmal and persistent arms will be analyzed separately. [REDACTED]
[REDACTED]
[REDACTED]
[REDACTED]

[REDACTED]
[REDACTED]
[REDACTED]
[REDACTED]

[REDACTED]
[REDACTED]
[REDACTED]
[REDACTED]
[REDACTED]
[REDACTED]

[REDACTED]
[REDACTED]
[REDACTED] all subjects

will be followed for 12 months, and a final report will be prepared for each arm.

Unless specified, the objectives are identical for the paroxysmal and persistent arms of the study.

Primary objective results by age, sex, race, and site will be provided in the final report.

12.2.2. Primary Safety Objective

Demonstrate an acceptable safety profile of PVI ablation with the PFA system.

Hypothesis

The following hypothesis will be tested in a one-sided test:

Ho: PS \geq 13%

Ha: PS < 13%

Where PS is the probability of a safety event through 6 months.

Endpoint Definition

The primary safety endpoint definition, as follows, is identical for each arm (paroxysmal AF and persistent AF) of the Pivotal Phase.

The following PFA system-related and ablation PFA procedure-related serious adverse events (SAEs), as adjudicated by the Clinical Events Committee (CEC), will be considered a primary safety event:

Within 6 months post-ablation:

- Pulmonary vein stenosis (>70% diameter reduction)
- Phrenic nerve injury/diaphragmatic paralysis (ongoing at 6 months)
- Atrioesophageal fistula

Within 30 days of ablation procedure:

- Cardiac tamponade/perforation
- Cerebrovascular accident
- Major bleeding requiring transfusion
- Myocardial infarction
- Pericarditis requiring intervention
- Transient ischemic attack
- Vagal nerve injury resulting in esophageal dysmotility or gastroparesis
- Vascular access complications requiring intervention
- Death
- Any PFA system-related or PFA procedure-related cardiovascular and/or pulmonary adverse event that prolongs or requires hospitalization for more than 48 hours (excluding recurrent AF/AFL/AT)

Analysis Methods

The probability of a safety event at 6 months (183 days) will be estimated using survival analysis, the Kaplan-Meier method. The standard error will be approximated using Greenwood's formula. A two-sided 95% log-log confidence interval for the probability will be constructed.

For every treated subject, day 0 is defined as the day of the index ablation procedure. For subjects with a safety event, the survival date will be set to the onset date of the safety event. For subjects without a safety event, those subjects will be censored at the last study contact date recorded on CRF which may include the last study visit, the exit date, or death date. If a subject without a safety event is lost to follow-up, the censoring date will be set to the last known study visit date.

Safety events related to a repeat ablation procedure with the PFA system will not be counted as safety events against the primary safety objective. However, all repeat PVI ablations using the PFA system and the safety events associated with them will be reported separately.

Performance Requirements

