8.9. Scheduled Follow-up Visits

After receiving notice of a completed index ablation procedure, Medtronic will provide the target dates and windows for each visit to the site. Should a subject miss a visit or the visit fall outside the pre-specified window, a study deviation must be reported and the original follow-up schedule maintained for subsequent visits.

Data analyses include follow-up visits, regardless of whether the visit occurs within the window. Therefore, a late visit is preferred over a missed visit but must be accompanied by a deviation. Follow-up visit windows are listed in Table 8 and are based on days after the index ablation procedure.

Table 8: Follow-up Schedule

Occurrence/ Visit	Window (Calculated days after the ablation procedure)	
	Window Start	Window End
Enrollment/Baseline ¹	-30 days	Day 0
Index PFA System Ablation Procedure	Day 0	Day 0
30 day	30 days	44 days
3 month	91 days	105 days
6 month	183 days	197 days
12 month	365 days	395 days

¹Note: if the time between the consent date and the procedure exceeds 30 days, the subject must be re-evaluated against inclusion and exclusion criteria to ensure they still qualify for the study.

Multiple modes of data collections may be employed to support the collection of required visit data at the 3- and 6-month visits such as: In office patient clinic visit, direct to patient contact (i.e. telephone, email, mail contact, etc.), and remote technology transmissions/uploads.

The following information is required to be collected at the follow-up visits:

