8.9.3. Six Month Visit

- Review medications
- Adverse event assessment
- Review symptoms suggestive of recurrent AF/AT/AFL
- 12-lead ECG
- Remind subject of instructions on patient activated ambulatory monitoring equipment for weekly and symptomatic transmissions
- Only in the case of suspected PV stenosis, is cardiac MRI or CT scan required. It is not required at this visit if it was already completed at an earlier visit where PV stenosis was confirmed.
- 24h continuous monitoring with Holter
- EQ-5D and AFEQT Questionnaires

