10.4. Reporting of Adverse Events, including Death

[figure not shown]
Reporting of Adverse Events to Medtronic will occur on an Adverse Event (AE) eCRF, including a description of AE, date of onset of AE, date of awareness of study site, treatment, resolution, assessment of both the seriousness and the relatedness to the investigational system and/or procedure. Each AE must be recorded on a separate AE eCRF. Exceptions include:

- Documented pre-existing conditions are not considered AEs unless the nature or severity of the condition has worsened. Additionally, arrhythmia episodes that are not new or worsening conditions and for which no action is taken are not reportable as AEs.
- Unavoidable Adverse Events, listed in Table 10 need not be reported unless the adverse event worsens or is present outside the stated timeframe after the ablation procedure.
- Cardioversions (DC or Drug) for recurrent symptomatic atrial fibrillation and other atrial arrhythmias are not considered serious adverse events

For any changes in status of a previously reported adverse event (i.e. change in actions taken, change in outcome, change in relatedness), an update to the original AE must be provided. All adverse events must be followed until the adverse event has been recovered / resolved, the subject exits the study or until study closure, whichever occurs first.

In the event that a subject is exited from the study prior to study closure, all efforts should be made to continue following the subject until all procedure or system related adverse events that are not resolved, as classified by the Investigator, are recovered / resolved.

At the time of study exit, all adverse events with an outcome of "not recovered / not resolved", "recovering / resolving" or "unknown" must be reviewed and updates provided as applicable.

All reported adverse events will be reviewed by a Medtronic representative. AEs will be classified according to the definitions provided.

Upon receipt of adverse events at Medtronic, a Medtronic representative will review the adverse event for completeness and accuracy and when necessary will request clarification and/or additional information from the Investigator. Medtronic will utilize MedDRA, the Medical Dictionary for Regulatory Activities, to assign a MedDRA term for each adverse event based on the information provided by the Investigator.

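### Does Section 12.2.2 under-count 6-month safety events because it has no dating rule for a late-found PV stenosis or an unresolved phrenic injury?

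*Combined protocol and SAP*

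**What the plan says.** Section 12.2.2 of the combined protocol and SAP reads the safety rate at a fixed day: "The probability of a safety event at 6 months (183 days) will be estimated using survival analysis, the Kaplan-Meier method". On dating it says: "For subjects with a safety event, the survival date will be set to the onset date of the safety event". Of subjects without an event it says "those subjects will be censored at the last study contact date recorded on CRF". The objective is met if the upper limit of the two-sided 95% log-log interval (Greenwood standard error) is below 13%.

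PV stenosis counts if it occurs within 6 months. Phrenic injury counts only if ongoing at 6 months. Table D-1 in Appendix D adds that it must be documented as present at 6 months or later, and defines it by fluoroscopy or sniff test. The Clinical Events Committee (CEC) adjudicates endpoint events (Sections 11.2 and 12.2.2).

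Four other places bear on the point:

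- Section 8.9: "Follow-up visit windows are listed in Table 8 and are based on days after the index ablation procedure". Table 8 puts the 6-month visit at days 183 to 197. The visit may be remote: "Multiple modes of data collections may be employed to support the collection of required visit data at the 3- and 6-month visits".
- Section 8.9.3: "Only in the case of suspected PV stenosis, is cardiac MRI or CT scan required". Neither that section nor Table 7 lists a test of phrenic function.
- Section 10.4: the adverse event form has separate fields, "including a description of AE, date of onset of AE, date of awareness of study site, treatment, resolution". For subjects who leave early, "all efforts should be made to continue following the subject until all procedure or system related adverse events that are not resolved" have recovered.
- Section 12.2.3 (effectiveness): recurrences found by monitoring at the in-window 12-month visit are reset to day 365, and a tipping-point analysis covers early exits. Section 12.2.2 has neither.

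**The concern.** The estimate is read on the day the visit window opens, so 14 of the 15 in-window visit days fall after it. If a site entered the visit or scan date as the onset of a stenosis first noticed then, the event would fall outside the 6-month rate although the 6-month assessment found it. A phrenic injury that is unresolved when the subject leaves, or is never retested, cannot meet the documentation requirement, so the subject is censored as event-free.

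Both effects lower the observed rate. The study is single-arm and unblinded, and the pass limit is one event wide in each arm. A dating convention chosen once a case is known would be chosen with its effect in view. The reset rule in Section 12.2.3 makes the absence of a counterpart in Section 12.2.2 look like an oversight.

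**Working it through.** **1. The plan's own figure.** Inputs from Section 12.2.2: true rate 5%, goal 13%, one-sided alpha 0.025, exact binomial. At n = 138 the largest passing count is 10: P(X ≤ 10 | 13%) = 0.0236 and P(X ≤ 10 | 5%) = 0.914. At n = 137 the limit is 9 and power is 0.851. The stated 138 is reproduced.

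**2. Pass limits at the actual arm sizes** (150 persistent, 165 paroxysmal; Section 12.2.4). Without censoring, S = 1 − x/n, v = √[x/(n(n − x))] / |ln S|, and the upper limit is 1 − S^exp(1.96v).

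- 11/150: √[11/(150 × 139)] = 0.02297, |ln S| = 0.07616, v = 0.3016; upper limit 12.85%, pass.
- 12/150: 13.66%, fail.
- 12/165: 12.45%, pass.
- 13/165: 13.18%, fail.

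**3. What one uncounted event does.** Allow 4 early exits per arm by day 183. This follows from 5% yearly attrition, uniform over days 1 to 364: 5% × 182/364 = 2.5%, which is 3.75 of 150 and 4.1 of 165.

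- At the limit: with 11 of 150 events counted, a stenosis dated day 190 leaves the estimate at 7.3% (upper 12.85%). Dated day 183, it gives 8.0% (upper 13.7%).
- Near the planned 5% rate, persistent arm: 7 events give an upper limit of 9.5%; one more gives 10.4% and two more at most 11.3%.
- Near the planned 5% rate, paroxysmal arm: 8 events give 9.5%; two more give 11.0%.

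The result changes only at the boundary.

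**4. How many events could go uncounted.** The documents give no rate, so these are assumptions based on Table 4.

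- *Phrenic injury, early exit:* 0.4% (top of the Table 4 range for permanent paralysis) × 2.5% = 0.01 percentage point, or 150 × 0.0001 = 0.015 events.
- *Phrenic injury, extreme:* every case at 0.4% is never reassessed, 0.40 point.
- *Stenosis, apparent figure:* 1% (top of Table 4), with onset spread evenly over 197 days, puts 1% × 14/197 = 0.07 point on days 184 to 197. These have true onset after day 183, and a 183-day endpoint is right to exclude them. The figure does not measure misdating.
- *Stenosis, relevant figure:* 1% × q, where q is the share with onset by day 183 but recorded as day 184 or later. The documents give no q. For example, q = 25% gives 0.25 point, or 150 × 0.0025 = 0.375 events.

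Probability of passing at a true rate of 13%, by points missed (binomial, limits 11 and 12):

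| Points missed | Basis | n = 150 | n = 165 |
|---|---|---|---|
| 0 | none | 0.0203 | 0.0142 |
| 0.01 | phrenic, early exit | 0.0204 | 0.0143 |
| 0.08 | with the 14/197 figure added (0.12 events in 150) | 0.0217 | 0.0153 |
| 0.25 | a quarter of stenoses misdated | 0.0248 | 0.0178 |
| 0.40 | every phrenic case never reassessed | 0.0280 | 0.0203 |
| 0.47 | 0.40 plus the 14/197 figure | 0.0296 | 0.0216 |
| 1.00 | every stenosis misdated | 0.0446 | 0.0338 |

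**5. What the text already decides.** For stenosis, pivotal-phase scans follow suspicion, so a symptom or finding normally precedes the image. The date that governs is onset, which the form separates from awareness. The CEC reviews supporting documents before setting final classifications (Section 11.2). Losing such an event requires a site to enter the scan date as onset and nobody to correct it; nothing in the plan tells them to do so. For phrenic injury, Table D-1 requires documentation at 6 months or later, and Section 12.2.2 censors anyone without an event. Together they give a definite answer. An injury confirmed late still counts, at an onset near day 0.

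**The case for a change.** The strongest case for a change is that a rule is cheap, the margin is one event, and both gaps lean the same way. No visit is scheduled between day 105 (the end of the 3-month window) and day 183, so first detection of stenosis could cluster at the 6-month visit. The misdated share might then be well above what evenly spread onset suggests. Section 12 also allows analysis changes that do not alter a principal feature to be explained only in the study report.

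Part of this stands. The visible Section 12.2.2 has no onset convention for a stenosis first noticed at the 6-month visit, and the misdated share is unknown. Late detection is not late onset, however, and the plan dates by onset.

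The comparison with Section 12.2.3 is weaker than it looks. The reset there handles rhythm monitoring required of every subject at a visit whose window opens on day 365, so without it nearly all such findings would be lost. Safety has no scheduled 6-month scan in the pivotal phase.

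The extreme phrenic bound needs every case to escape follow-up of unresolved events, the review at exit, the efforts after exit (Section 10.4), and the adverse event assessment at 12 months, a visit for which the plan offers no remote option. Counting every injury without documented recovery would also change the endpoint from ongoing at 6 months to not shown to have recovered. That is a debatable redefinition, and it could count injuries that did recover.

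Finally, Section 5.3 promises a statistical analysis plan before data are analysed, and much of Section 12.2.1 is redacted. A convention may exist outside the visible text.

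**Conclusion.** The plan is silent on one detail of stenosis dating, and its default for undocumented phrenic injury leans towards the device. Neither undermines the safety conclusion. Under the existing onset rule, the CEC and analysts can date a late-found stenosis sensibly, and the phrenic case is already classified by the definition and the censoring rule.

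The phrenic loss from early exit is about 0.01 point, which moves the chance of wrongly passing from 0.0203 to 0.0204 (n = 150) and from 0.0142 to 0.0143 (n = 165). Adding the overstated stenosis figure gives only 0.0217 and 0.0153. In the persistent arm 0.025 is exceeded only if more than about a quarter of stenoses at Table 4's upper rate are misdated, or if nearly two thirds of phrenic cases at 0.4% escape all follow-up (0.25/0.40 = 62.5%). The paroxysmal arm stays below 0.025 even at 0.47 point. At the planned 5% rate, one or two extra events do not alter the result in either arm.

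This rests on Table 4's upper rates applying to this device, on the plan's 5% uniform attrition, and on sites recording onset as the form asks. It is a gap in detail that can be filled in practice, so no change to the plan is called for.

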³² Aryana, A., Baker, J., Espinosa Ginic M., et al. Posterior wall isolation using the cryoballoon in conjunction with pulmonary vein ablation is superior to pulmonary vein isolation alone in patients with persistent atrial fibrillation: A multicenter experience. *Heart Rhythm* 15, 1121-1129 (2018).

medical journals. Note, these studies are the same studies utilized in rationales below for effectiveness performance criteria.

Varying complication rates are observed, and varying definitions of complication were used in each study, but to test a novel catheter ablation technology, an objective performance criterion (OPC) of 13% provides a reasonable margin to compare the PFA system against ablation technologies currently used to treat AF.

Figure 4: Current Safety Rates in Catheter Ablation Technologies for Paroxysmal AF and Persistent AF

[figure not shown]

Table 14: Summary of Published Literature on Safety Rates of Catheter Ablation for AF

Reference	AF Type	Ablation Catheter Type	Subjects	Reported Safety Rate (95% CI) ⁱ
STOP AF PAS P100010/R017 "STOP AF PAS Final Report". ²⁴	Paroxysmal	Cryo	354	5.8% (3.6 – 8.8)
FIRE AND ICE Kuck KH, et al. N Engl J Med. 2016; 374:2235-45. ²⁵	Paroxysmal	Cryo	374	10.2% (7.3 – 13.7)
Squara F, et al. Europace. 2015;17:718-24. ²⁶	Paroxysmal	Cryo	178	7.3% (3.9 – 12.2)
Schmidt M, et al. Int J Cardiol. 2013;167:114-120. ²⁷	Paroxysmal	Cryo	124	Not reported
Providencia R, et al. Europace. 2017;19:48-57. ²⁸	Paroxysmal	Cryo	393	5.9% (3.8 – 8.7)
FIRE AND ICE Kuck KH, et al. N Engl J Med. 2016; 374:2235-45. ²⁵	Paroxysmal	RF	376	12.8% (9.6 – 16.6)
Squara F, et al. Europace. 2015;17:718-24. ²⁶	Paroxysmal	RF	198	7.1% (3.9 – 11.6)
Providencia R, et al. Europace. 2017;19:48-57. ²⁸	Paroxysmal	RF	467	4.9% (3.1 – 7.3)
HeartLight Dukkipati S, et al. J Am Coll Cardiol. 2015;66:1350-60. ²⁹	Paroxysmal	VGLB	167	5.3% (2.4 – 9.9)
CRYO4PERSISTENT AF Boveda S, et al. J Am Coll Cardiol. [Epub ahead of print]. ³⁰	Persistent	Cryo	101	4.0% (1.1 – 9.9)
1STOP Tondo C, et al. Heart Rhythm. 2017;15:363-368. ³¹	Persistent	Cryo	434	4.3% (2.6 – 6.7)
Aryana et al. Heart Rhythm 2018;15:1121-1129. ³²	Persistent	Cryo	168 (PVI only)	2.4% (0.6 – 6.0)
STAR AF II Verma A, et al. N Engl J Med. 2015;372:1812-22. ¹³	Persistent	RF	67 (PVI only)	6.0% (1.7 – 14.6)

ⁱ95% confidence interval calculated using binomial exact methods

Rationale for Timing of the Final Safety Analysis

The PFA system is a novel catheter ablation technology, but analogous in procedural use to currently approved catheter ablation systems for the treatment of AF. The major complications related to traditional catheter ablation systems will describe the safety profile of the PFA system. The 2017 HRS/EHRA/ECAS Expert Consensus Statement on Catheter and Surgical Ablation of Atrial Fibrillation acknowledges that "AF ablation is an invasive procedure that entails risks, most of which are present during the acute procedural period. However, complications can also occur in the weeks or months following ablation." Symptoms and complications associated with AF ablation are stratified by those that occur within 1 month post-ablation and those that occur more than 1 month post-ablation.³ To evaluate the safety profile of the PFA system, the primary safety events in this study align with the recognized AF ablation complications. Recognizing that most AF ablation complications present acutely, Medtronic proposes that the safety profile of the PFA system will be established with 6-month follow-up data. The study will continue to collect, analyze and report all adverse events for all subjects through 12 months follow-up.

Sample Size Calculation

A sample size of 138 treated subjects followed for 6 months affords 90% power based on the following assumptions:

- 6-month safety rate = 5% (desired rate for new catheter ablation technology)
- OPC = 13% at 6 months
- Overall alpha = 0.025, one-sided
- One final analysis
- Binomial exact methods

The primary analysis will utilize Kaplan-Meier survival methods. Binomial exact methods were utilized for sample size and power calculations, as with very low expected attrition, Kaplan-Meier and binomial methods yield very similar results.

Determination of Subjects/Data for Analysis

All Primary Analysis Cohort subjects (only their index PFA procedure) will be included.

12.2.3. Primary Effectiveness Objective

Objective

Demonstrate an acceptable chronic effectiveness of PVI ablation with the PFA System, based on freedom from treatment failure.

Hypotheses

For the paroxysmal AF arm:

Ho: PS \leq 55%

Ha: PS $>$ 55%

For the persistent AF arm:

Ho: PS \leq 40%

Ha: PS $>$ 40%

Where PS is the probability of treatment success at 12 months.

Endpoint Definition

The definition of treatment success and failure differs slightly between the paroxysmal and persistent arms of the Pivotal Phase.

Primary Effectiveness Endpoint for Paroxysmal AF

Treatment success is defined as freedom from treatment failure. The study requires 24-hour Holter monitoring at 6 and 12 months in addition to weekly and symptomatic patient activated ambulatory monitoring transmissions from 3 through 12 months, and 12-lead ECGs at all follow up visits. Treatment failure is defined as any of the following components:

- Acute procedural failure (see definition below)
- Documented AF/AT/AFL on Holter/patient activated ambulatory monitoring/12-lead ECG after the 90-day post-ablation blanking period
- Minimum of 30 seconds on Holter/patient activated ambulatory monitoring or 10 seconds on 12-lead ECG recording
- Note: Documented occurrence and treatment of typical right-sided cavotricuspid isthmus dependent atrial flutter is not considered a failure.
- Any subsequent AF surgery or ablation in the left atrium, except for repeat PVI ablations using PFA within the 90-day blanking period.
- Direct current cardioversion for atrial tachyarrhythmia recurrences after the 90-day blanking period.
- Class I or III antiarrhythmic drug (AAD) use after the 90-day blanking period.

Blanking period is defined as the first 90 days after the index ablation procedure. Recurrences of atrial arrhythmias during the blanking period will not be counted in the determination of the first clinical failure for the primary endpoint. Within the blanking period, recurrent arrhythmias can be managed with antiarrhythmic drugs or cardioversions. Titration of Class I and III antiarrhythmic medications are allowed during the blanking period.

Acute procedural failure is defined as:

- Inability to isolate all accessible targeted pulmonary veins (minimally assessed for entrance block and, where assessable, exit block) during the index procedure
- Ablation using a non-study device to isolate any pulmonary vein

Primary Effectiveness Endpoint for Persistent AF

Treatment success is defined as freedom from treatment failure. The study requires 24-hour Holter monitoring at 6 and 12 months in addition to weekly and symptomatic patient activated ambulatory monitoring transmissions from 3 through 12 months, and 12-lead ECGs at all follow up visits. Treatment failure is defined as any of the following components:

- Acute procedural failure (see definition below)
- Documented AF/AT/AFL on Holter/patient activated ambulatory/12-lead ECG after the 90-day post-ablation blanking period
- Minimum of 30 seconds on Holter/patient activated ambulatory or 10 seconds on 12-lead ECG recording
- Note: Documented occurrence and treatment of typical right-sided cavotricuspid isthmus dependent atrial flutter is not considered a failure.
- Any subsequent AF surgery or ablation in the left atrium, except for repeat PVI ablations using PFA within the 90-day blanking period.
- Direct current cardioversion for atrial tachyarrhythmia recurrences after the 90-day blanking period.
- Class I or III antiarrhythmic drug (AAD) dose increase from the historic maximum ineffective dose (prior to the ablation procedure) or initiation of a new Class I or III AAD after the 90-day blanking period. Note: remaining on the same pre-ablation dose or decreased dose of a previously failed or not tolerated Class I or III AAD after the 90-day blanking is not considered a failure.

Blanking period is defined as the first 90 days after the index ablation procedure. Recurrences of atrial arrhythmias during the blanking period will not be counted in the determination of the first clinical failure for the primary endpoint. Within the blanking period, recurrent arrhythmias can be managed with antiarrhythmic drugs or cardioversions. Titration of Class I and III antiarrhythmic medications are allowed during the blanking period.

Acute procedural failure is defined as:

- Inability to isolate all accessible targeted pulmonary veins (minimally assessed for entrance block and, where assessable, exit block) during the index procedure
- Ablation using a non-study device to isolate any pulmonary vein

Analysis Methods

The probability of a subject achieving effectiveness success at 12 months (365 days) will be estimated using survival analysis, the Kaplan-Meier method. The standard error will be approximated using Greenwood's formula. A two-sided 95% log-log confidence interval for the probability will be constructed.

For every treated subject, day 0 is defined as the day of the index ablation procedure. For subjects with treatment failure, the survival date will be set to the date of the treatment failure. For subjects without treatment failure through 12 months, those subjects will be censored at the last study contact date recorded on a CRF which may include the last study visit, the last weekly patient activated ambulatory, the exit date, or death date. If a subject without a treatment failure is lost to follow-up, the censoring date will be set to the last known study visit date.

For the component of the endpoint, documented AF/AT/AFL, if this documentation resulted from rhythm monitoring occurring at the 12-month visit within the 12-month visit window, the date of recurrence will be set to 365 days from the study ablation procedure so that these events will be counted as treatment failures in the 12-month Kaplan-Meier analysis.

Sensitivity Analyses

A sensitivity analysis will be conducted to estimate the potential impact of subjects with less than 12 months of follow-up at the final analysis. The mortality rate in this patient population is anticipated to be low. The total assumed attrition rate through one year is 5%. Because the primary endpoint will be tested using survival methods, all treated subjects are included in the primary analysis, and therefore no subjects will have complete missing data. For subjects that exit early, a tipping point analysis will be conducted to estimate the potential impact of subjects with less than 12 months of follow-up. These subjects will be defined as subjects with partial data. The tipping point analysis methods will be as follows. For each subject with less than 12 months of follow-up, each subject will be set to treatment failure (failure date set to date of study exit). The 12-month Kaplan-Meier estimate will be re-calculated with the earliest (closest to index ablation) sequentially added to the Kaplan-Meier analysis, and the results presented in table format. The tipping point will be defined as the number of additional failures in which the performance goal (55% for paroxysmal and 40% for persistent) is crossed by the lower 95% confidence bound.

Performance Requirements

If the lower bound of the confidence interval (coverage level determined by the alpha spending function) is greater than the performance goal (55% for paroxysmal and 40% for persistent), the objective will be considered met.

Rationale for Performance Criteria (Paroxysmal)

[figure not shown]
Traditionally, the choice of acceptable effectiveness performance criteria for paroxysmal AF with 12-month follow-up data is selected based on the 2017 HRS/EHRA/ECAS Expert Consensus Statement on Catheter and Surgical Ablation of Atrial Fibrillation, which provides recommendations for success rates in clinical trials. The recommendation for evaluating the effectiveness of a treatment for paroxysmal AF is as follows: *"If minimum chronic success rate is selected as an objective effectiveness endpoint for a clinical trial, we recommend that the minimum chronic acceptable success rate for paroxysmal AF at 12-month follow-up is 50%."*³ Medtronic proposes a single-arm, non-randomized paroxysmal AF study is appropriate with performance criteria that is established based on effectiveness rates for currently approved ablation catheters (RF ablation, cryoablation, and VGLB ablation), in addition to the recommendation provided by the 2017 Expert Consensus Statement.

Figure 5 and Table 15 display effectiveness rates observed in current clinical trials studying approved catheter ablation technologies in paroxysmal AF patients. Included are published literature where the search criteria include publications of large multi-centered studies where the therapy was the use of catheter ablation (RF ablation, cryoablation, or VGLB ablation) for a PVI-only approach for paroxysmal AF. The summary includes study results published as manuscripts in peer reviewed medical journals. Varying rates in 12-month effectiveness have been observed. Similarly, variations in definitions of primary effectiveness and variations in arrhythmia monitoring have been utilized. The proposed PULSED AF study design has an aggressive definition of primary paroxysmal AF effectiveness (requiring acute success and disallowing AAD use and reablations) and a more rigorous study design (requiring weekly patient activated ambulatory monitoring through 12 months).

To test a novel catheter ablation technology, under these study design requirements, an OPC of 55% provides a reasonable margin to compare the PFA system against current approved ablation technologies.

Figure 5: Current 12-Month Effectiveness Rates in Approved Catheter Ablation Technologies for Paroxysmal AF

[figure not shown]

Table 15: Summary of Published Literature on Catheter Ablation for Paroxysmal AF

Reference	Design	Sites	Subjects (Ablation Type)	Subject Monitoring (When/How)	Effectiveness Endpoint Assessment	Acute Procedural Success	6M Effectiveness ^{i,ii}	12M Effectiveness ⁱ
STOP AF PAS P100010/R017 "STOP AF PAS Final Report". ²⁴	prospective, single arm	39	354 cryo	ECG @ 3M, 6M, 12M; 24hr Holter @ 6M; 48hr Holter @ 12M; Symptomatic event recorder for 30 days	AF/AFL/AT > 30s; Intervention for AF	98.0%	89% (85-92)	80% (75-84)
FIRE AND ICE Kuck KH, et al. N Engl J Med. 2016; 374:2235-45. ²⁵	randomized (RF and cryo), noninferiority	16	374 cryo	ECG and 24hr Holter @ 3M, 6M, 12M; Weekly and symptomatic TTM	AF/AFL/AT > 30s; AAD use; Reablation	98.9%	81% (77-85)	65% (60-70)
Squara F, et al. Europace. 2015;17:718-24. ²⁶	Consecutive, non-randomized, ambidirectional (prospective and retrospective)	4	178 cryo	ECG and 24hr Holter @ 1M, 3M, 6M, 9M, 12M; Symptomatic 24hr Holter	AF/AFL/AT >30s	100%	88% (82-92)	82% (76-87)
Schmidt M, et al. Int J Cardiol. 2013;167:114-120. ²⁷	Consecutive patients	3	124 cryo	ECG and 72hr Holter @ 1M, 3M, 6M, 9M, 12M; Symptomatic event recorder	AF or Flutter >30s	100%	86% (79-92)	66% (57-74)
Providencia R, et al. Europace. 2017;19:48-57. ²⁸	Consecutive, prospective, non-randomized	6	393 cryo	ECG and 24hr Holter @ 1M, 3M, 6M, 9M, 12M; Symptomatic ECG and 24hr Holter	Any AF/AT >30s; AAD use	99.0%	89% (85-92)	82% (78-86)
FIRE AND ICE Kuck KH, et al. N Engl J Med. 2016; 374:2235-45. ²⁵	randomized (RF and cryo), noninferiority,	16	376 RF	ECG and 24hr Holter @ 3M, 6M, 12M; Weekly and symptomatic TTM	AF/AFL/AT > 30s; AAD use; Reablation	97.9%	82% (78-86)	64% (59-69)
Squara F, et al. Europace. 2015;17:718-24. ²⁶	Consecutive, non-randomized, ambidirectional (prospective and retrospective)	4	198 RF	ECG and 24hr Holter @ 1M, 3M, 6M, 9M, 12M; Symptomatic 24hr Holter	AF/AFL/AT >30s	100%	89% (84-93)	84% (78-89)
Providencia R, et al. Europace. 2017;19:48-57. ²⁸	Consecutive, prospective, non-randomized	6	467 RF	ECG and 24hr Holter @ 1M, 3M, 6M, 9M, 12M; Symptomatic ECG and 24hr Holter	Any AF/AT >30s; AAD use	97.6%	82% (78-85)	73% (69-77)
HeartLight Dukkipati S, et al. J Am Coll Cardiol. 2015;66:1350-60. ²⁹	Randomized (RF and VGLB), prospective	19	167 VGLB	ECG @ 1M, 3M, 6M, 9M, 12M; 24hr Holter @ 6M, 12M; Symptomatic and weekly TTM	AF >1 min; Atypical/unknown AFL/AT; AAD use	97.7%	75% (68-81)	61% (53-68)
Weighted average (weights based on study sample sizes)							84.5%	73.2%

ⁱ Confidence interval calculated with binomial Fisher's exact method

ⁱⁱ 6-month effectiveness rates are estimated from survival curves published in literature

Rationale for Performance Criteria (Persistent)

The choice of acceptable effectiveness performance criteria for persistent AF with 12-month follow-up data is selected based on the 2017 HRS/EHRA/ECAS Expert Consensus Statement on Catheter and Surgical Ablation of Atrial Fibrillation, which provides recommendations for success rates in clinical trials. The recommendation for evaluating the effectiveness of a treatment for persistent AF is as follows: *"If minimum chronic success rate is selected as an objective effectiveness endpoint for a clinical trial, we recommend that the minimum chronic acceptable success rate for persistent AF at 12-month follow-up is 40%."*³

Additionally, there is mounting evidence in published literature on the use of catheter ablation in the treatment of persistent AF. Figure 6 and Table 16 display a summary of published literature where the search criteria were publications of large multi-centered studies where the therapy was the use of catheter ablation (RF ablation or cryoablation) for a PVI-only approach for persistent AF. The summary includes study results published as manuscripts in peer reviewed medical journals. Varying rates in 12-month effectiveness have been observed. Similarly, variations in definitions of primary effectiveness and variations in arrhythmia monitoring have been utilized. The PULSED AF study design has an aggressive definition of primary persistent AF effectiveness (requiring acute success; and disallowing re-ablations, AAD dose increase from the historic maximum ineffective dose, or initiation of new AAD) and a more rigorous study design (requiring weekly patient activated ambulatory monitoring through 12 months).

To test a novel catheter ablation technology under these study design requirements, the Expert Consensus Statement recommended OPC of 40% provides a reasonable margin to compare the PFA system against ablation technologies currently used to treat persistent AF.

Figure 6: Current 12-Month Effectiveness Rates in Catheter Ablation Technologies for Persistent AF

[figure not shown]

Table 16: Summary of Published Literature on Catheter Ablation for Persistent AF

Reference	Design	Sites	Subjects (Ablation Type)	Subject Monitoring (When/How)	Effectiveness Endpoint Assessment	Acute Procedural Success	6M Effectiveness ⁱ	12M Effectiveness ⁱ
CRYO4PERSISTENT AF Boveda S, et al. J Am Coll Cardiol. [Epub ahead of print]. ³⁰	prospective, single-arm, interventional post-market clinical study	11	101 cryo	ECG @ 3M, 6M, 12M and 48hr Holter @ 6M, 12M	AF/AFL/AT > 30s; Reablation	98.0%	81% (72-88)	61% (51-71)
1STOP Tondo C, et al. Heart Rhythm. 2017;15:363-368. ³¹	Prospective, single-arm	35	434 cryo	ECG and Holter @ 3M, 6M, 9M, 12M	AF > 30s; Reablation	98.5%	81% (77-84)	64% (59-69)
Aryana et al. Heart Rhythm. 2018;15:1121-1129. ³²	Consecutive, double-arm non-randomized	≤7	168 cryo (PVI only)	ECG @ 3M, 6M, 12M; 2-week TTM @ 6 weeks and 3-6 months	AF/AFL/AT > 30s	99.3%	67% (59-74)	47% (39-55)
STAR AF II Verma A, et al. N Engl J Med. 2015; 372: 1812-1822. ¹³	Prospective, triple-arm randomized,	48	67 RF (PVI only)	ECG and 24hr Holter @ 3M, 6M, 9M, 12M; Weekly and symptomatic TTM	AF > 30s; Reablation	97.0%	81% (70-90)	60% (47-72)
Weighted average (weights based on study sample size)							77.9%	59.5%

ⁱ Confidence interval calculated with binomial Fisher's exact method

ⁱⁱ 6-month effectiveness rates are estimated from survival curves published in literature, with the exception of the CRYO4PERSISTENT manuscript, which reported the 6-month effectiveness rate

Determination of Subjects/Data for Analysis

All Primary Analysis Cohort subjects will be included.

Sample Size Calculation

Given the separation of primary effectiveness objectives for paroxysmal AF and persistent AF, the study sample size is powered independently for paroxysmal AF and persistent AF arms.

For both arms, the sample size was computed using a simulation program. Given the assumptions below, the program ran through 10,000 simulations of this study for each potential sample size. The lowest sample size (going by units of 5 subjects) where at least 9000 studies were successful (i.e., power >90%) was chosen as the sample size for that arm.

The simulation program took into account the [REDACTED], alpha boundaries, the enrollment rate, and other assumptions listed below. Where percentages are assumed, it gave each simulated subject that chance of the event occurring (e.g., each simulated subject had a 2% chance of having an acute failure). It performed the primary effectiveness objective's analysis as stated above on each simulated study to determine whether that study would have been successful [REDACTED]

Assumptions (Paroxysmal Arm)

- The overall alpha will be 0.025, [REDACTED]
- Power=90%
